8.3.3. Analysis of Primary Efficacy Variable

8.3.3.1. Primary Analysis

Participants will be analyzed according to randomized treatment. Descriptive statistics of WAIS-IV Coding test score, percent change from baseline and change from baseline will be summarized by treatment group and by visit.

The primary endpoint is change from baseline to Day 42 in the WAIS-IV Coding test and this primary endpoint will be analyzed using a mixed-effects model for repeated measures (MMRM). The model will include baseline WAIS-IV Coding test score as a continuous explanatory variable, treatment, visit, and visit-by-treatment interaction as categorical explanatory variables. The Kenward-Roger correction to degrees of freedom will be applied. All explanatory variables will be treated as fixed effects in the model, and all post-baseline time points will be included in the model. An unstructured (UN) covariance matrix with the default Newton-Raphson algorithm used by SAS PROC MIXED will be used to model the within-subject correlation. If this model fails to converge – or, if the convergence criteria is met but the final Hessian is not positive definite - the Fisher Scoring algorithm (via the SCORING option of the PROC MIXED statement), the no-diagonal factor analytic structure (via the TYPE=FA0(T) option of the REPEATED statement, where T is the total number of time points), Toeplitz, Autoregressive (1) [AR (1)], Compound symmetry (CS) covariance structure will be used, following this sequence until convergence is achieved. If the model still does not converge with CS structure, no results will be reported. When the covariance structure is not UN, the sandwich estimator for the variance-covariance matrix will be derived, using the EMPIRICAL option in the PROC MIXED statement in SAS. The primary comparison will be between SAGE-718 and placebo at the Day 42. LSM and SE with 95% CI for each treatment group as well as difference in LSM and SE with 95% CI will be summarized, and the p-value from the hypothesis test of no difference between the treatment groups will be also presented.

Line plots with LSM and SE bars of change from baseline in WAIS-IV Coding test score over time by treatment group will be provided.

By-participant listing of WAIS-IV Coding test score by treatment group and by visit will be produced.

8.3.3.2. Multiplicity adjustment:

Not applicable.

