8.3.3.3.1. Control-Based Pattern Mixture Model Multiple Imputation

If $\geq 10\%$ of participants have missing data in the primary endpoint, a sensitivity analysis using control-based Pattern Mixture Model Multiple Imputation (PMM-MI) under the missing not at random (MNAR) assumption will be used to investigate the impact of missing data (Lingling 2019, SAS Institute Inc.). MNAR assumes the missingness depends on the unobserved study data and cannot be predicted solely based on participant's observed data.

In cases where there is a missing baseline value, the missing baseline value will not be imputed with control-based PMM-MI. Instead, the average of all available baseline values (regardless of treatment group) will be populated for the missing baseline value. After this step, the control-based PMM-MI will be applied. Control-based PMM-MI under MNAR involves four steps as described below.

Step 1. Assessing the pattern of missing data.

To investigate the pattern of missing data, "ods output misspattern" will be used in the MI procedure of the SAS system (PROC MI). The imputation method will be based on the observed pattern of missing data and amount of missing data. The pattern of missing data will be assessed as monotone or arbitrary.

Step 2. Turning the arbitrary missing patterns to monotone missing patterns under missing at random (MAR) assumption.

If a mixture of non-monotone and monotone missing patterns exist in the data with majority of monotone missing patterns, then the arbitrary missing patterns will be converted to monotone missing patterns under MAR assumption.

Step 3. Generation of imputed datasets for AVAL using control-based pattern imputation under MNAR.

PROC MI will be used to generate m complete datasets. The selection of m depends on the required computing time and will be determined based on the amount of missing information prior to the last patient last visit but has been recommended varying from 5 to 100.

Step 4. Convert datasets into long format in which CHG variable represents all change from baseline with different values of avisit.

Step 5. Conducting model-based analysis using each imputed dataset.

The m complete datasets are analyzed using MMRM.

Step 6. Pooling the results from the imputed m datasets for inference.

The results from the m complete datasets are combined to produce inferential results.

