8.3.3.3.2. Tipping Point Analysis

If $\geq 10\%$ of participants have missing data in the primary endpoint, another sensitivity analysis – tipping point analysis – will be considered to investigate the robustness of the result to departures from the MAR assumption of the MMRM model and to identify the tipping point

where the treatment effect in participants with missing data overturns the treatment effect from statistically significant to statistically non-significant.

Hence the tipping point analysis will only be performed if the primary efficacy analysis is statistically significant in treatment effect.

Implementing the tipping point approach includes the following steps ([Yuan 2014](#), [SAS Institute Inc.](#)):

Step 1. Missing baseline will be imputed as the mean of non-missing baseline for all other participants. For post-baseline, under the MNAR assumption, missing WAIS-IV Coding test score up to Day 70 will be imputed using PROC MI under MNAR.

Step 2. The imputed values for observations in SAGE-718 treatment group will be adjusted directly using the shift parameter (δ).

Step 3. The imputed datasets with the shift parameter applied will be analyzed using PROC MIXED.

Step 4. The results will be combined for the inference using PROC MIANALYZE.

Step 5. Step 1-4 will be repeated until the result is not statistically significant.

Step 6. If needed, step 1-5 will be repeated with more stringent shift parameter applied until the result is not statistically significant.

The shift parameter (δ) value will be progressively decreased, and process repeated until non-significant p-value is achieved. One hundred datasets will be generated.

The tipping point summary for each pairwise comparison will include LSM difference, the 95% CI, and p-value for each of δ value. Iterations including the tipping point will be summarized.

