APPENDIX B. DETAILS OF STATISTICAL METHODOLOGY

Sample SAS Code for MMRM

```
proc mixed data= data;
  class trt01pn(ref='1') avisitn usubjid;
  model CHG = trt01pn base avisitn trt01pn *avisitn/ddfm=kr;
  repeated avisitn / subject= usubjid type=UN;
  lsmeans trt01pn*avisitn / diff=all cl alpha=0.05;
run;
```

Sample SAS Code for GEE

```
proc genmod data= data;
  class trt01pn(ref='1') avisitn usubjid;
  model AVALC = base trt01pn avisitn trt01pn *avisitn / dist=bin link=logit;
  repeated avisitn /subject= usubjid type=UN;
  lsmeans treatment*avisit / diff exp cl;
run;
```

Sample SAS Code for ANCOVA

```
proc mixed data= data;
  class trt01pn(ref='1');
  model CHG = trt01pn base / solution cl;
  lsmeans trt01pn / cl diff;
run;
```

Sample SAS Code for PMM-MI under MNAR

Step 1. Assessing the pattern of missing data

```
proc mi data=non_mono seed=xxx n impute=0;
  var trt01pn base y1-y3; *y1=Day 14, y2=Day 42, y3=Day 70;
  ods output misspattern=pattern;
run;
```

Step 2. Turning the arbitrary missing patterns to monotone missing patterns under MAR assumption

```
proc mi data=non_mono out=mono seed=xxx n impute=m
  min=.. x x x
  max=.. y y y; * period (.) means no imputation needed;
  var trt01pn base y1 y2 y3;
  mcimc chain=multiple impute=monotone;
run;
```

Step 3. Generation of imputed datasets for AVAL using control-based pattern imputation under MNAR

```
proc mi data=mono seed=xxx n impute=m out=imputed;
  min=. . x x x;
  max=. . y y y;
  by _imputation_;
  class trt01pn;
  var y1 y2 y3;
  monotone reg(/details);
  mnar model(y1 y2 y3/ modelobs=(trt01pn='1')); *only control group is used to derive
the imputation model;
run;
```

Step 4-1. Calculate CHG14, CHG42, and CHG70.

Step 4-2. Convert datasets into long format in which CHG variable represents all change from baseline with different values of avisit.

Step 5. Conducting model-based analysis using each imputed dataset

```
proc mixed data= imputed;
  by _imputation_;
  class subjid trt01pn(ref='1') avisitn;
  model chg = trt01pn base avisitn trt01pn*avisitn / ddfm=kenwardroger;
  repeated avisitn / subject=usubjid type=UN;
  lsmeans trt01pn*avisitn / diff=all cl alpha=0.05;
  ods output lsmeans=lsmeans diff=diffs;
run;
```

Step 6. Pooling the results from the imputed *m* datasets for inference

```
proc sort data=lsmeans;
  by trt01pn avisitn _imputatoin_;
run;

proc mianalyze parms=lsmeans;
  modeleffects estimate;
  ods output ParameterEstimates=lms;
  by treatment avisit;
run;

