proc sort data=diffs;
  by avisit _imputatoin_;
run;

proc mianalyze parms=diffs;
```

```
modeleffects estimate;  
ods output ParameterEstimates=dif;  
by avisit;  
run;
```

Sample SAS Code for Tipping Point Analysis

```
/*-----*/  
/*--- Generate imputed data set for specified shift parameters ---*/  
/*--- data= input data set ---*/  
/*--- smin= min shift parameter ---*/  
/*--- smax= max shift parameter ---*/  
/*--- sinc= increment of the shift parameter ---*/  
/*--- out= output imputed data set ---*/  
/*-----*/  
%macro midata( data=, smin=, smax=, sinc=, out=);  
  data &out;  
  set _null_;  
run;  
  
/*----- # of shift values -----*/  
%let ncase= %sysevalf( (&smax-&smin)/&sinc, ceil );  
/*----- Imputed data for each shift -----*/  
%do jc=0 %to &ncase;  
  %let sj= %sysevalf( &smin + &jc * &sinc);  
  proc mi data=&data seed=xxx nimpute=m out=outmi;  
    class trt01pn;  
    monotone reg(y1 y2 y3);  
    mnar adjust( y1 y2 y3 / shift=&sj adjustobs=(trt01pn='1') ); *active treatment is used;  
    var trt01pn y1 y2 y3;  
  run;  
  
  data outmi;  
    set outmi;  
    Shift= &sj;  
  run;  
  
  data &out;  
    set &out outmi;  
  run;  
%end;  
%mend midata;
```

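### Multiple-imputation pooling drops the Kenward-Roger degrees of freedom, so pooled intervals are about 2% narrower than a small-sample rule gives and the tipping point lies slightly too far out

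*SAP*

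**What the plan says.** **Primary analysis.** SAP 8.3.3.1 says "The Kenward-Roger correction to degrees of freedom will be applied".

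**Control-based imputation (PMM-MI).** In Appendix B, Step 5 fits each imputed data set with "model chg = trt01pn base avisitn trt01pn*avisitn / ddfm=kenwardroger". Step 6 pools with "proc mianalyze parms=lsmeans" for the LS means and "proc mianalyze parms=diffs" for the treatment differences. Neither call has an `EDF=` option. The text of 8.3.3.3.1 says only "The results from the m complete datasets are combined to produce inferential results". It leaves the number of imputations m open: it "has been recommended varying from 5 to 100".

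**Tipping point.** SAP 8.3.3.3.2 says "The results will be combined for the inference using PROC MIANALYZE" and "One hundred datasets will be generated". It names no options. The sample tipping-point code in Appendix B ends after the imputation step, so no analysis or pooling call is shown.

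Both analyses depend on at least 10% of participants lacking the primary endpoint. The tipping point also requires a significant primary result.

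**The concern.** PROC MIANALYZE does not pick up the df computed by PROC MIXED. Unless they are supplied through `EDF=`, it takes the complete-data df as infinite and bases the pooled t reference on m and the fraction of missing information alone. This is software behaviour, which the SAP does not describe. The correction requested at Step 5 is therefore dropped at Step 6.

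In a trial of this size the complete-data df are small enough to matter a little. Two things are at stake:

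- Part of any difference between the primary and a sensitivity result would come from the reference distribution, not from the missing-data assumption under test.
- The tipping-point search stops at the first non-significant shift. A critical value that is too small lets the search run further and makes the result look more robust than it is.

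**Working it through.** **Inputs from the SAP.** Section 5.2 gives 60 evaluable, 20% dropout and 76 randomised 1:1. Check: 60/(1 − 0.20) = 75, raised to 76 for equal arms of 38. The effect size is 0.8/1.07 = 0.748, and a two-sample t-test with 30 per arm at 0.75 has 81.5% power against the stated 80%. The plan gives no figure for pooled df or interval width, so there is none to reproduce.

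**Assumptions.** Complete-data df v = 76 − 3 = 73 (two arm means and a baseline slope), because every imputed data set is complete; low case 60 − 3 = 57. Missing-information fraction λ = 0.1 to 0.2, with a wider range of 0.02 to 0.30. Neither v nor λ is in the documents.

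**Formulas.**

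- Default: v_m = (m − 1)/λ²
- Barnard-Rubin, which `EDF=` invokes: v_obs = [(v + 1)/(v + 3)]·v·(1 − λ), then v_BR = 1/(1/v_m + 1/v_obs)
- Narrowing = 1 − t(v_m)/t(v_BR), at the 97.5% point

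**Worked case, m = 100, λ = 0.2, v = 73.** v_m = 99/0.04 = 2,475. v_obs = (74/76)·73·0.8 = 56.9. v_BR = 55.6. The critical values are 1.961 and 2.004, so narrowing is 2.1%.

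| v | m | λ | v_m | v_BR | t default | t Barnard-Rubin | narrower |
|---|---|---|---|---|---|---|---|
| 73 | 100 | 0.1 | 9,900 | 63.6 | 1.960 | 1.998 | 1.9% |
| 73 | 100 | 0.2 | 2,475 | 55.6 | 1.961 | 2.004 | 2.1% |
| 73 | 5 | 0.2 | 100 | 36.3 | 1.984 | 2.028 | 2.15% |
| 57 | 100 | 0.2 | 2,475 | 43.3 | 1.961 | 2.016 | 2.75% |

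For v = 73 and λ of 0.1 to 0.2, a nominal 5% test runs at 5.4% to 5.5%. Over v = 57 to 73 and λ = 0.02 to 0.30, narrowing runs from 1.7% to 3.2%. At m = 5 the default reference is not close to normal, but the Barnard-Rubin df fall as well, so the gap stays near 2%.

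**Simulation, 38 per arm, Day 42 values missing.**

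| Imputation | Missing | m | Mean λ | Narrower | Null rejection, default | Null rejection, Barnard-Rubin |
|---|---|---|---|---|---|---|
| MAR | 20% | 5, 20, 100 | 0.18–0.19 | 2.1–2.2% | 5.4–5.5% | 4.9–5.1% |
| MAR | 10% | 100 | 0.09 | 1.9% | 4.9% | 4.8% |
| Control-based | 20% | 5, 20, 100 | 0.15–0.16 | 2.0–2.1% | 2.1–2.4% | 1.9–2.2% |
| Control-based | 10% | 100 | 0.085 | 1.9% | 3.4% | 2.8% |

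The rejection rates carry Monte Carlo error. Under control-based imputation, Rubin's variance is conservative before any df question arises.

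**Tipping shift, in SD units, m = 100.** Take SE = √(2/38)/√(1 − λ). Assume a shift δ on the missing fraction p of the active arm moves the estimate by p·δ and leaves the SE unchanged. The tipping size is then (d − t·SE)/p. With p = 0.20, λ = 0.2 and d = 0.75, SE = 0.2565:

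- Default: (0.75 − 1.9609 × 0.2565)/0.20 = 1.235
- Barnard-Rubin: (0.75 − 2.0036 × 0.2565)/0.20 = 1.180
- Gap: 0.055 SD, or 4.4% of the default value

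With d = 0.60 the values are 0.485 and 0.430, an 11.3% gap. Across 10% to 20% missing and λ from 0.05 to 0.20 (to 0.15 at 10% missing), the gap is 2.9% to 4.4% for d = 0.75 and 6.1% to 11.3% for d = 0.60. In absolute terms it is 0.04 to 0.06 SD at 20% missing and 0.08 to 0.10 SD at 10%.

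**The case against.** The strongest case against is that this is labelled sample code and visibly unfinished. It misspells the imputation index, and its pooling steps sort results by variable names that do not match the model. A missing option there is weak evidence of a decision to use infinite df. That is fair, but the text of 8.3.3.3.1 and 8.3.3.3.2 supplies no rule either, so the final programs have nothing to correct the omission.

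Three further points limit the concern:

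- No tipping-point pooling call is shown. The effect there is inferred from 8.3.3.3.2 naming the procedure, plus its default. The shift increment is also unspecified, so the gap could be less than one grid step.
- The sample tipping-point code shifts treatment code 1, which the PMM-MI code uses as control, while 8.3.3.3.2 says SAGE-718. That is a separate and larger problem; it neither causes nor cancels this one.
- SAP 8.3.3.3 calls for discussion only when a sensitivity result changes direction, and df cannot do that.

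A reader might also infer three stronger things that do not hold:

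- **That the error favours the sponsor in both missing-not-at-random analyses.** The control-based intervals over-cover even with default df, so they are narrow only relative to Barnard-Rubin intervals.
- **That intervals are 2.4% to 2.8% too narrow, with correct df of 40 to 50.** At λ = 0.2 this needs a complete-data N near 60 to 68. Imputed data sets hold up to about 76 participants, and taking a near-evaluable N and then applying the (1 − λ) factor counts much of the missingness twice.
- **That with almost no missing data the pooled result would be a z-test unable to match the primary p-value.** The 10% trigger excludes that case.

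**Conclusion.** The inconsistency is real and minor. As written, the PMM-MI pooling replaces the Kenward-Roger df by (m − 1)/λ², and the tipping-point pooling would do the same if run with defaults. The main figure, about 2% at the planned size, rests on assumed complete-data df near 73 and λ of 0.1 to 0.2.

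Only the tipping point is affected in an anti-conservative direction, and only a borderline result would read differently. For the control-based analysis the issue is comparability with the primary analysis, not coverage. The primary result is untouched.

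**What to change.** Add `EDF=` to every PROC MIANALYZE call. For the treatment differences, use the mean Kenward-Roger df of the Day 42 contrast over the imputed data sets; for the LS means, use the matching df. Write out the missing tipping-point analysis and pooling code with the same option.

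State the rule in one sentence each in 8.3.3.3.1 and 8.3.3.3.2 before database lock. Fixing m for PMM-MI at the same time would remove the other open element of the pooled df.

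The cost is one option per call and slightly wider intervals. The control-based analysis becomes a little more conservative than it already is.

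### The tipping-point analysis uses monotone regression with no step to make the missing pattern monotone, and its Step 1 wording conflicts with its stated MAR aim and its own code

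*SAP*

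**What the plan says.** SAP 8.3.3.3.2 considers a tipping-point analysis when at least 10% of participants lack the primary endpoint, and adds a second condition: "Hence the tipping point analysis will only be performed if the primary efficacy analysis is statistically significant in treatment effect". The stated purpose is to test how the result stands up to departures from the MAR assumption of the MMRM. In Step 1 a missing baseline is set to the mean, and for post-baseline visits "missing WAIS-IV Coding test score up to Day 70 will be imputed using PROC MI under MNAR". Step 2 then shifts the imputed SAGE-718 values. The text fixes 100 datasets.

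The Appendix B macro does Steps 1 and 2 in one procedure call. Its main lines are:

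- "proc mi data=&data seed=xxx nimpute=m out=outmi"
- "monotone reg(y1 y2 y3"
- "mnar adjust( y1 y2 y3 / shift=&sj adjustobs=(trt01pn='1') ); *active treatment is used"
- "var trt01pn y1 y2 y3"

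A comment in the control-based code gives the order: y1 is Day 14, y2 is Day 42 and y3 is Day 70.

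The control-based analysis in SAP 8.3.3.3.1 also uses monotone regression, but only after its own Step 2. If monotone and non-monotone patterns are mixed, with monotone in the majority, "then the arbitrary missing patterns will be converted to monotone missing patterns under MAR assumption". Appendix B supplies an MCMC call for this and runs the next call separately for each imputation.

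**The concern.** Monotone regression fills each visit from the variables before it in order. It presumes that once a visit is missing, all later ones are missing too. A participant with no Day 14 score but a Day 42 score breaks that order. So does one with no Day 42 score but a Day 70 score, and there the gap is the primary endpoint itself. The SAP provides for such patterns in one sensitivity analysis and not in the next, which uses the same method on the same data.

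Step 1 has a second problem. A tipping-point analysis asks how far the imputed values must move from MAR before significance is lost, so the unshifted values should be MAR values. Text that says they "will be imputed using PROC MI under MNAR" before any shift leaves the starting point unclear.

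At stake is whether this analysis can be run and read as planned after a positive result. It is the one sensitivity analysis in the SAP that reports how large a departure from MAR would overturn that result.

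**Working it through.** **1. The plan's own figure.** SAP 5.2 gives 30 evaluable per arm, 20% dropout and about 76 randomized. 30 / 0.8 = 37.5, which rounds up to 38 per arm, and 2 × 38 = 76. This reproduces. The stated 80% power also holds: at effect size 0.75 with 30 per arm, the two-sided t-test at 0.05 (58 degrees of freedom) has 81.5% power.

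**2. Is the analysis likely to be triggered?** The conditions are at least 10% missing and a significant primary result. The plan anticipates 20% dropout and 80% power, so both are expected if its planning assumptions hold.

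**3. Chance that a non-monotone record occurs.** Let q be the share of participants who miss Day 14 or Day 42 and return later. The documents give no value, so q is assumed. Chance of at least one among N = 1 − (1 − q)^N.

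| q (assumed) | N = 60 | N = 76 | Expected records in 76 (76 × q) |
|---|---|---|---|
| 0.5% | 26% | 32% | 0.4 |
| 1% | 45% | 53% | 0.8 |
| 2% | 70% | 78% | 1.5 |
| 5% | 95% | 98% | 3.8 |

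Returning after a gap is possible by design, because participants who stop IP are asked to keep attending (SAP 5.1). The Day 28 contact is by phone only and carries no Coding test.

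**4. What the coded shift is measured from.** The macro has treatment in the variable list, does not restrict which arm informs the model, and adds the shift to values drawn from that regression. A large simulated trial was run with assumed inputs: Day 42 effect 0.75 SD, Day 14 effect half of that, correlation 0.6, and 20% dropping out at random after Day 14.

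- Shift 0: 0.75 SD, the MAR result.
- Shift −1 SD on active: expected 0.75 + 0.20 × (−1) = 0.55; simulated 0.56.

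So zero shift in the code is a MAR imputation. Baseline is not in the macro's variable list but is in the MMRM, so the code conditions on less than the primary model does.

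**5. Which arm is shifted.** The macro labels `trt01pn='1'` as active. The control-based code in the same appendix uses that value for the control group, and the MMRM code uses it as the reference level. If 1 is control, lowering the shift raises the effect: 0.75 − 0.20 × (−1) = 0.95 SD at −1 (simulated 0.95), and the result would never tip.

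**6. Why the conversion step needs a rule on the shift.** A Day 42 value filled during conversion is no longer missing in the second call, so it would escape the shift. In an arm of 38, one such participant changes the arm mean by 1/38 = 0.026 SD per 1 SD of shift, against 0.20 SD from the planned 20% missing.

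**The case against.** **The code is labelled as a sample, and its input is a parameter.** The control-based analysis has the same 10% trigger, so a converted dataset may already exist to feed in. This stands in part. But the SAP does not make the link, and the macro does not run by imputation, so stacked copies of each participant would be pooled as if they were separate records. The macro also leaves the number of imputations as m.

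**The rates are assumed, and the analysis windows reduce gaps.** SAP 8.3.2 widens Day 14 to Days 2–28 and Day 42 to Days 29–56, and maps in unscheduled and early-termination visits. This stands: the percentages above precede any such filling, and the chance of one awkward record says nothing about its effect on the result.

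**Sensible repairs hardly differ.** This largely stands. In a simulation with assumed inputs (38 per arm, 20% missing Day 42, two participants missing Day 14 only, correlation 0.7, 150 trials), MAR conversion and a fully conditional variant differed in the Day 42 z by 0.00 at shift 0 and 0.01 at −1 SD. Only dropping those participants mattered (mean absolute change in z about 0.17 to 0.18), and SAP 8.1 says all participants and all non-missing data are used.

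**Stronger readings that the documents do not support.** A reader might infer from Step 1 that the shift is measured from the control-based model in 8.3.3.3.1. Section 8.3.3.3.2 does not name that model and the macro does not code it. The MNAR wording can refer to the procedure's shift statement. A reader might also take this as the plan's main evidence of robustness, but control-based, complete-data and per-protocol analyses are planned too. Nor must the repair be chosen unblinded: missing patterns can be seen before the blind is broken, which happens only after database lock.

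**Conclusion.** The concern holds as a gap in specification. The text and macro apply monotone regression without the conversion step that the SAP itself uses for the same method. As written, they cannot process a missed Day 14 or Day 42 visit followed by observed data. At assumed rates of 1% to 5%, at least one such record among 76 has a 53% to 98% chance before window mapping.

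The Step 1 wording is a conflict between text, aim and code. It is not evidence that the coded shift starts away from MAR.

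Severity is minor. The primary analysis is untouched, two conditions must be met before this analysis runs, and a reasonable repair probably changes the numbers little. The arm-code discrepancy could matter more and should be settled in the same edit. The documents show two conflicting labels for one code, not which is correct.

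**What to change.** Before database lock, replace the post-baseline part of SAP 8.3.3.3.2 Step 1 with:

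> Make the missing pattern monotone under MAR by MCMC as in 8.3.3.3.1 Step 2 (100 sets). Then impute the remaining values under MAR with treatment and baseline in the model, one imputation per set (BY _imputation_).

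Keep the shift in Step 2, so that shift 0 is the MAR result. State whether values filled in the conversion step, in particular a missed Day 42 with Day 70 observed, receive the shift.

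In the Appendix B macro, put in the same two calls, run the second by imputation, add baseline to the variable list, and set the number of imputations to match the text. Reconcile the treatment code in the shift statement with the control-based code, so that the shift falls on SAGE-718 as Step 2 states.

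The cost is one SAP paragraph and one added PROC MI call. No sample size or primary-analysis figure changes.

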8.3.1. Definition of Efficacy Variables

8.3.1.1. Primary Efficacy Assessment

The WAIS-IV Coding test is a valid and sensitive measure of cognitive dysfunction impacted by many domains that correlates with real-world functional outcomes (e.g., the ability to accomplish everyday tasks) and recovery from functional disability. In-clinic administration of the WAIS-IV Coding test will use the traditional paper-and-pen format, in which the participant is required to identify the symbols matched to numbers using a key and write in the symbol beneath the associated number. The score is based on the total number of codes correctly completed over a 120 second time limit (higher scores reflecting better performance).

WAIS-IV Coding Test is collected at Baseline (Day -7), Day 1 (pre-dose), Day 14, Day 42 and Day 70.

[REDACTED]

A series of horizontal black bars of varying lengths, with a few small vertical black marks on the left side.

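### SAP Appendix B labels `trt01pn='1'` as control in one MNAR program and as active treatment in the other, so one of the two sensitivity analyses targets the wrong arm

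*SAP*

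**What the plan says.** SAP Section 8.3.3.3.2 describes the tipping-point analysis. On the arm it says: "The imputed values for observations in SAGE-718 treatment group will be adjusted directly using the shift parameter". On the direction it says that the shift parameter "value will be progressively decreased, and process repeated until non-significant p-value is achieved". SAP Section 8.3.1.1 fixes the direction of benefit: the Coding score counts correct codes "over a 120 second time limit (higher scores reflecting better performance").

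Appendix B then gives sample SAS code. In the tipping-point macro, the MNAR statement reads "adjustobs=(trt01pn='1') ); *active treatment is used". In Step 3 of the control-based pattern mixture program it reads "mnar model(y1 y2 y3/ modelobs=(trt01pn='1')); *only control group is used to derive" the imputation model. Both programs select the same value of the same variable.

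The MMRM and GEE code both declare "class trt01pn(ref='1') avisitn usubjid", and Step 5 of the control-based program declares "class subjid trt01pn(ref='1') avisitn". The ANCOVA code uses the same reference level. Neither document says which arm is coded 1.

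**The concern.** One code value cannot denote both arms. These two programs are the plan's only analyses of the primary endpoint that replace the missing-at-random assumption, and one of them must act on the wrong arm.

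The consequence depends on the coding. If 1 is placebo, the tipping-point program lowers imputed placebo scores on a scale where higher is better. The SAGE-718 advantage then grows as delta falls, and an analysis meant to challenge a positive result would appear to confirm it. If 1 is SAGE-718, the tipping-point program is right, but the control-based program fits its imputation model to the drug arm and so is no longer control-based.

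**Working it through.** **1. The two codings, side by side**

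| If `trt01pn='1'` is | Control-based imputation (Step 3) | Tipping-point macro |
|---|---|---|
| placebo | correct | wrong: shifts placebo, while Section 8.3.3.3.2 shifts SAGE-718 |
| SAGE-718 | wrong: model fitted to the drug arm | correct |

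Neither row makes both programs correct. This step needs no assumption. Placebo is the likelier meaning of 1, because all the model code uses it as the reference level; that is an inference.

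**2. Inputs from the plan's sample size (SAP Section 5.2)**

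The effect size is 0.8/1.07 = 0.748, stated as 0.75. With 30 per arm and two-sided alpha 0.05, a two-sample t-test at 0.75 has 81.5% power, consistent with the stated 80%. For dropout, 30/(1 - 0.20) = 37.5, so 38 per arm and 76 in total, as stated.

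**3. Effect of the shift on the Day 42 difference**

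Let D be the SAGE-718 mean minus the placebo mean, with m of n values imputed in the shifted arm. Adding delta to those values at Day 42 moves that arm's mean by (m/n) × delta. So D changes by

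- +(m/n) × delta if SAGE-718 is shifted (the SAP text);
- -(m/n) × delta if placebo is shifted (the code, if 1 = placebo).

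The 10% trigger is 0.10 × 76 = 7.6, so 8 participants, or 4 per arm if balanced. The 12-missing row is an assumption.

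| Missing per arm | m/n | Change in D per -1 of delta, SAGE-718 shifted | Same, placebo shifted |
|---|---|---|---|
| 4 of 38 (trigger) | 0.105 | -0.11 | +0.11 |
| 8 of 38 (about 20%) | 0.211 | -0.21 | +0.21 |
| 12 of 38 | 0.316 | -0.32 | +0.32 |

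**4. Effect on significance, by simulation**

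Assumptions, none of them in the documents except 38 per arm and the 0.75 effect: true effect 0.75 SD of change at Day 42 and half that at Day 14; equal correlation of 0.6, 0.8 or 0.9 among baseline, Day 14 and Day 42; 4, 8 or 12 missing at Day 42 in each arm; delta in SD of change or in raw-score SD. That makes 18 settings, each with 200 trials that were significant at delta 0. Missing values were imputed 20 times by Bayesian regression on arm, baseline and Day 14, shifted at Day 42, analysed by ANCOVA on change and pooled by Rubin's rules.

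One setting (correlation 0.8, 8 missing per arm, SD of change; D = 0.81 at delta 0):

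| Delta | SAGE-718 shifted: D (lost significance) | Placebo shifted: D (lost significance) |
|---|---|---|
| -1 | 0.60 (38%) | 1.02 (0%) |
| -2 | 0.39 (78%) | 1.23 (0%) |
| -3 | 0.18 (98%) | 1.44 (0%) |

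Across all 18 settings, the share losing significance with placebo shifted was 0% at -1, -2, -3 and -5 SD. With SAGE-718 shifted by -1 SD of change it was 8-16% (4 missing), 37-38% (8) and 56-64% (12). With delta in raw-score SD the ranges were 14-42%, 37-80% and 58-98%.

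**5. A single worked data set**

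This used 100 imputations, a full-data difference of 0.75, a Day 14 to Day 42 correlation of about 0.5 and 8 of 38 missing per arm. At delta 0, p = 0.0035. With SAGE-718 shifted, p = 0.036 at -1 and 0.098 at -1.5, so it tips between them. With placebo shifted, p = 0.0004 at -1 and 0.0001 at -2; it does not tip.

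**The case against.** The strongest reply is that the governing text is right and only sample code is wrong. Section 8.3.3.3.2 names SAGE-718. The Appendix B blocks are templates with placeholder seeds and imputation counts and blank shift limits, and a programmer must complete them against the text. That stands as a limit on the harm. It does not remove the contradiction, because the code and its comments are what a programmer will adapt.

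Second, a bias towards SAGE-718 also requires negative delta, and the macro leaves the shift range blank. A positive shift on placebo would move the difference against SAGE-718. This is fair as to the macro, but the text decreases delta until significance is lost, which points to negative values.

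Third, the main simulation is not the sample code. It imputes on baseline, shifts Day 42 only, and uses 20 imputations and ANCOVA, whereas the code omits baseline and shifts every visit, and the text calls for 100 data sets and PROC MIXED. It also assumes equal missingness by arm. A further run imputed without baseline and shifted both Day 42 and Day 70, and it included 1 missing on placebo against 7 on SAGE-718. With placebo shifted, 0% lost significance at -1 and -3 SD of change; with SAGE-718 shifted, 17-42% did at -1 and 65-98% at -3. The direction holds. What remains of the point is that with few placebo values missing the wrong-arm shift does little (1/38 = 0.026 per unit of delta), and with none it does nothing. The analysis is then uninformative rather than favourable to the drug.

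Fourth, a difference that grows at each step would be noticed. Probably so, but possibly only after database lock, when SAP Section 2 requires changes to be documented and discussed in the study report.

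**Conclusion.** The concern holds. Under either coding, one of the two MNAR programs selects the wrong arm; this follows from the code comments alone.

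That the error lies in the tipping-point program and favours SAGE-718 rests on two readings: 1 = placebo, inferred from the reference level, and negative delta, taken from Section 8.3.3.3.2. Under both, the sign of the shift's effect is reversed, and the analysis cannot tip in the intended direction at any plausible negative delta. Only this direction and the 0% loss of significance are stable; the other percentages vary with the assumed correlation, missingness and SD unit. The 18 settings stop at -5 SD. A separate check at correlation 0.8, with 4 or 8 missing per arm, also gave 0% at -10 and -20 SD. In other settings, variance inflation at extreme shifts could still remove significance.

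The reach is limited. Both MNAR analyses depend on at least 10% missing primary data, which the planned 20% dropout makes likely. The tipping-point analysis carries a further condition: "Hence the tipping point analysis will only be performed if the primary efficacy analysis is statistically significant in treatment effect". The primary MMRM, complete-data and per-protocol analyses are unaffected. The error should be fixed, but it does not threaten the primary result.

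**What to change.** Before database lock:

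1. Define the `trt01pn` codes once, at the top of Appendix B.
2. Set `adjustobs` in the tipping-point code to the SAGE-718 code, as Section 8.3.3.3.2 requires.
3. Confirm that `modelobs` in Step 3 of the control-based code points to placebo, and correct it if it does not.

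These steps are right under either coding. The cost is one definition line and one code value in the SAP, with no change to data collection or trial conduct.
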